7.0 Regulatory Requirements

Prior to the start of the study, the following documents will be collected and filed:

- Signed protocol signature page
- Curriculum vitae of the PIs and Sub-investigators, updated within 2 years
- Current medical licenses for the PIs and all Sub-investigators
- Financial disclosure form signed by the PIs and all Sub-investigators listed on the
- Copy of the IRB approval letter for the study and the IRB Membership List
- Investigator Agreement

Investigators Obligations

Drs. [name] and [name] will be responsible for ensuring that all study site personnel, adhere to all FDA regulations and guidelines regarding clinical trials, including guidelines for GCP (including the archiving of essential documents), both during and after study completion. Additionally, they will be responsible for the subject's compliance to the study protocol.

All information obtained during the conduct of the study with respect to the patients' state of health will be regarded as confidential. This is detailed in the written information provided to the patient. An agreement for disclosure of any such information will be obtained in writing and will be signed by the patient.

Informed Consent

The investigators will obtain and document informed consent for each patient screened for this study. All patients will be informed in writing of the nature of the protocol and investigational therapy, its possible hazards, and their right to withdraw at any time, and will sign a form indicating their consent to participate prior to the initiation of study procedures.

Institutional Review Board

This protocol and relevant supporting data were submitted and approved by the UCSF IRB (UCSF, Human Research Protection Program, [name], FWA#00000068; IRB Registration 00000229, [name], HRRP Director, please see **Appendix G**). Amendments to the protocol will also be submitted to the IRB prior to implementation of the change. The PI is responsible for informing the IRB of the progress of the study and for obtaining annual IRB renewal. The IRB must be informed at the time of completion of the study and should be provided with a summary of the results of the study by the PI. The PI must notify the IRB in writing of any SAE or any unexpected AE according to ICH guidelines.

Data safety monitoring board (DSMB) and safety monitoring plan

Treatment emergent adverse events that are assessed by the principal investigators as possibly, probably, or definitely related to surgical implantation or chronic cortical recording AND are unexpected or meet seriousness criteria (death, immediately life threatening, hospitalization >24 hours, persistent or significant disability, or significant intervention required to prevent one of the previously-stated outcomes) will be recorded and reported to the IRB, device manufacturer and the FDA via the MedWatch online voluntary reporting form within 10 working days of the study team's knowledge of the event.

All such events will also be reported to the data safety monitor board (DSMB), led by [name], a neurosurgeon at our home institution, who does not have direct involvement in this study but who has expertise in implantable devices, pain management and neurosurgery. The DSMB will meet regularly to review data related to the clinical trial, provide guidance and feedback, and review any adverse event reports. Treatment-related adverse events assessed as definitely, probably, or possibly related to study procedures and either serious or unexpected, noted by any study personnel will be reported within 10 working days of their knowledge of the event to the DSMB. The DSMB will then advise the PI on potential changes in procedures to improve safety. The safety endpoint will consist of all adverse events.

Throughout the clinical trial, should a serious adverse event occur that is assessed to be surgery or stimulation-related, or related to the presence of the DBS leads, such as focal seizure or motor weakness congruent with device localization or infection, in discussion with the patient and DSMB, a decision will be made regarding the possibility of lead removal and the study being halted for the patient. Removal will be accomplished by re-opening the original incisions and grasping the lead at or just posterior to the burr hole originally used for placement.

Furthermore, if there is a serious surgery or stimulation-related adverse event, or if the patient reports greater than 25% increased pain (post-surgery recovery period compared to pre-surgery) or onset of suicidality, the study will be halted for the patient.

If two patients meet one or more of these criteria (i. serious surgery or stimulation-related adverse event, ii. greater than 25% increase pain, or iii. onset of suicidality), the study will be halted until information is reviewed by the DSMB and FDA.

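### The 10-working-day FDA and manufacturer report does not name stimulation, and the 25% pain halt, if applied as a relative change on a bounded score, cannot trigger from 80% of the maximum upward

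*Combined protocol and SAP*

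**What the plan says.** All the safety rules at issue are in section 7.0 of the combined protocol and SAP.

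**Reporting.** Under the DSMB and safety monitoring plan, the 10-working-day report to the IRB, the device manufacturer and the FDA takes treatment-emergent events that are, in the principal investigators' judgement, at least possibly "related to surgical implantation or chronic cortical recording AND are unexpected or meet seriousness criteria". The DSMB report is wider: it takes events "related to study procedures and either serious or unexpected, noted by any study personnel will be reported within 10 working days". Under Institutional Review Board, "The PI must notify the IRB in writing of any SAE or any unexpected AE according to ICH guidelines". Under Investigators Obligations, the responsible investigators must ensure that site personnel "adhere to all FDA regulations and guidelines regarding clinical trials".

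**Halting.** A serious surgery- or stimulation-related event halts the study for that patient. So does worsening pain or new suicidality: "if the patient reports greater than 25% increased pain (post-surgery recovery period compared to pre-surgery) or onset of suicidality, the study will be halted". This, too, is a halt at the level of the individual. Once a second patient meets any of these criteria, "the study will be halted until information is reviewed by the DSMB and FDA".

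**Pain measures.** Section 2.0 requires a 30-day average above 5 on a 0-10 numeric rating scale (NRS) and sets no upper limit. Section 4.0 makes the pain VAS a primary measure. It is taken at baseline (visit 1.4) and at the Phase 1 clinic sessions after surgery.

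**The concern.** The reporting sentence lists two causes, and the device's therapeutic action is not one of them. The authors had wider terms to hand: the same section refers to study procedures for the DSMB report and to stimulation in the halt rules. Staff who follow the specific sentence would not send the FDA or the manufacturer a first serious event that they attribute to stimulation alone. Section 1.0 itself foresees a hazard of this kind, since EEG may be used in Phases 2 and 3 to check for subclinical seizure activity under stimulation.

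The pain halt names no instrument and no visits for the recovery period. If staff apply it as a relative change in a score, the scale's upper end limits how far a patient with severe pain can rise. For some patients the criterion could then never be met, however much worse they felt. The same criterion feeds the two-patient study halt, so such patients could not contribute to that rule through pain either.

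**Working it through.** The plan gives no sample size, power or alpha figure for this point, so there is none to reproduce. The 25% is a rule threshold.

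**Step 1: trace one event attributed only to stimulation.**

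| Recipient | Rule | Reached by a single event? |
|---|---|---|
| IRB | Any SAE or unexpected AE | Yes |
| DSMB | Serious or unexpected, related to study procedures | Yes, 10 working days |
| FDA | Related to implantation or chronic recording | Not named |
| FDA | Two patients meeting a halt criterion | No; needs a second patient |
| Manufacturer | Related to implantation or chronic recording | Not named |

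The two-patient rule counts serious surgery- or stimulation-related events. An unexpected but non-serious stimulation event would not reach the FDA by that route, and the rule does not mention the manufacturer.

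**Step 2: the ceiling of the pain rule.** Inputs are the threshold (more than 25%, section 7.0) and a maximum of 10. The 0-10 range is stated for the entry NRS. The range of the VAS is not stated, so 0-10 is an assumption.

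- Score that must be exceeded from baseline b: 1.25 × b.
- Largest possible relative rise: (10/b − 1) × 100.
- The rule can trigger only if 1.25 × b < 10, that is b < 10/1.25 = 8.

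| Baseline b | Must exceed | Largest rise | Can trigger? |
|---|---|---|---|
| 6 | 7.5 | 66.7% | Yes |
| 7 | 8.75 | 42.9% | Yes |
| 7.9 | 9.875 | 26.6% | Yes, with 10 − 9.875 = 0.125 points of room |
| 8 | 10.0 | 25.0% | No; the rise must be greater than 25% |
| 8.5 | 10.625 | 17.6% | No |
| 9 | 11.25 | 11.1% | No |

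**Step 3: other readings.**

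- On a 0-100 scale the cutoff is 100/1.25 = 80, again 80% of the maximum.
- If 25% means a quarter of the scale range, the score must exceed b + 2.5. That is 8.5 from 6, 9.5 from 7 and 10 from 7.5, so the rule cannot trigger from 7.5 upward.
- If the patient states the percentage increase directly, there is no ceiling.

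**The case against.** **On reporting**, the backstops are real. The IRB and DSMB routes cover a stimulation event. The general duty to follow FDA rules applies. An event judged even possibly related to implantation falls inside the sentence, and two serious cases bring FDA review. The appendices and the Investigator Agreement are not in the text supplied. A reader might infer that stimulation events go unreported; the documents do not support that. What stands is narrower: the general duty names no event, recipient or deadline, and the one sentence that does name them leaves stimulation out.

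**On pain**, the rule speaks of what the patient reports, which can mean a directly stated percentage. The ceiling is therefore conditional. The SAE and suicidality halts and the right to withdraw apply at any baseline, though none of them measures worsening pain. Three stronger readings are tempting and fail:

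- *That the NRS and the VAS are equal rivals for the rule.* The NRS is listed only at screening, while the pain VAS is a primary measure taken before and after surgery. The VAS is the natural default; what is missing is a statement that the rule uses it.
- *That the two-hour abstention from pain medication biases the comparison.* The visit schedule in section 3.0 gives that instruction from visit 5, at three weeks. The hospital and 10-day visits do not list it, and the recovery period may mean those.
- *That the protocol expects patients to start at 8 or more.* The 8-9 out of 10 under Progression of phases (section 3.0) is an example of narrow fluctuation during Phase 1, after implantation. It is not a pre-surgery baseline.

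**Conclusion.** Both points hold in limited form and merit a short amendment.

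1. The expedited report to the FDA and manufacturer does not name stimulation. The gap is one category of event: serious or unexpected, attributed to stimulation alone, in a single patient. This rests on the visible text.
2. Applied as a relative change on a bounded score, the pain halt has no effect from 80% of the maximum upward, and almost none just below it. The arithmetic is exact. Its relevance assumes a score-based reading, which the text neither states nor excludes. Eligibility permits such patients, but the documents give no baseline pain distribution, so the number affected cannot be estimated.

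A third matter is wording only. For surgery- or stimulation-related serious events, one sentence says "a decision will be made regarding the possibility of lead removal and the study being halted for the patient", while the next makes the patient-level halt mandatory. A reader might infer that the rules conflict. The second sentence can be read as the stricter rule, with lead removal left to discussion.

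**What to change.** **Reporting.** Change the relatedness wording to *surgical implantation, chronic cortical recording, stimulation or other study procedures*. Cost: slightly more reporting to the FDA and manufacturer.

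**Pain halt.** Apply the rule to the pain VAS already collected at visit 1.4 and after surgery, state its range, say that the 25% is relative, and name the visits that make up the recovery period. Add a patient-level trigger without a ceiling: marked worsening rated by the patient or a clinician and confirmed at a second contact, with *marked* defined in advance. Open it to all patients, so that there is no step at 8. Have the DSMB state in advance whether a confirmed report also counts in the two-patient rule. Cost: one short rating at those visits and possibly a few more patient-level halts. If confirmed reports do count, two of them would pause the whole study until DSMB and FDA review.

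**Wording.** Say that the halt is mandatory for surgery- or stimulation-related serious events and that discussion concerns lead removal and events related only to the presence of the leads. Cost: one sentence.
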